#### **Project phases**

The project includes 6 phases:

I phase - agreement in principle on the sampling method;

II phase - recruitment;

III phase - first sampling;

- IV phase training on perception and concordance;
- V phase second sampling to verify the progression of the agreement;
- VI phase third manual sampling and evaluation with Myoton.

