#### **Description of the phases**

I phase - The two examiners together with the principal investigator perform 2 hours of training to standardize the sampling method (localization of the point to be evaluated of the ITB and intensity of pressure of the fingertips to be used) and discussion on the tension gradation detected on the ITB with some volunteers.

II phase - The recruitment will be carried out through the search for volunteers among the students of the OSCE-Bologna school of osteopathy, through announcement in the classroom and publication of the

recruitment in the FB social group of the school (OSCE planet) and WhatsApp groups of students organized by year.

III phase - First sampling of manual evaluation only, using a sample of 40 subjects (both limbs), as proposed in the literature (Patijn 2019).

The operators identify if there is an equal or different stiffness between the right and left ITB.

There will be a double evaluation for each sampling session: 1) if there is a uniformity of the tension between the two sides, or if there is a prevalence on one side; 2) quantification of the difference, if present, with a graduation in 3 levels.

In the first sampling, the examiner will indicate with + 1 a greater tension on the right side; - 1 on the left side; 0 if there are no significant differences.

The second sampling consists in identifying, when present, the graduation of the tension difference between the two sides, arlTBrarily divided into 3 levels. The examiner will then report:

+ 3 to indicate more tension on the right with a large difference from the left;

+ 2 to indicate greater tension on the right with a medium difference compared to the left;

+ 1 to indicate more tension on the right with a slight difference from the left;

0 to indicate an insignificant prevalence of tension on one side with respect to the other;

- 3 to indicate greater tension on the left with a large difference compared to the right;

- 2 to indicate greater tension on the left with an average difference with respect to the right;

- 1 to indicate more tension on the left with a slight difference compared to the right.

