IV phase - The manual examiners carry out a period of training on perception and agreement, lasting about 20 hours. This training is done using tools (gold standard) made specifically to change the state of density and tension of elastic structures and ropes that simulate the ITB, connected to dynamometers to quantify the state of tension. In vivo evaluation, between operators, are used to verify the exact point of where to take the tension sample and compare the tension data obtained for the construction of the agreement.

V phase - The second sampling to verify the progression of manual agreement, as proposed in the literature (Patijn 2019), is carried out by evaluating the tension of the ITBs, with the same method as the first sampling with volunteers, but in a reduced sample (about 20 subjects). If from the statistical processing of the results of this trial evaluation a good improvement in the agreement is highlighted, compared to the previous sampling (baseline) weighted Cohen's K value greater than or equal to 0.60, the program moves on to the VI phase; otherwise, there will be additional training.

VI phase - The definitive manual sampling consists in repeating, using the same modality of the first evaluation (baseline), with different or identical subjects of the first sampling. The number of subjects will always be 40 evaluated by both examiners and each examiner will evaluate the same subject twice about 20-60 minutes apart. The same subjects will be tested, after the manual evaluation, with the Myoton using the

modality previously described. The results of the Myoton are automatically stored in the preset instrument with the subject ID and downloadable to the computer in an Excel worksheet.

All the data obtained is collected and processed by the examiner who does not participate directly in the data collection using an Excel spreadsheet and/or the R program.

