#### Settings

The samplings will be made in a room with two beds arranged about 3 meters apart and two desks. A screen, placed on both beds, will cover the examined subject from the pelvis upwards. The same subject is evaluated, on the same day, by both examiners twice, approximately 20-60 min apart.

Two subjects at a time are made to enter the room where the two manual examiners are present; a third examiner will use the Myoton.

When the 2 subjects enter the room and lie down in a supine position on the bed, with both limbs uncovered, the operator keeps their feet together, with a Velcro strap, to symmetrize the major axis of the feet and indirectly rotation of the hip.

During this preparation of the subjects to test, the manual examiners are turned away so as not to identify the test subjects. Once the positioning is complete, the examiners turn around and have 15 seconds to evaluate the assigned subject (see figures - examiner A always evaluates the subject on the right bed first while examiner B the one on the left); once the subject has been evaluated and the subject's identification code has been reported on a piece of paper with the result of the evaluation which is placed in a container, they go on to evaluate the subject lying on the opposite bed and repeat the same procedure for recording and storing the data detected.

Once the manual evaluation test has been carried out by both examiners, the subjects, before getting off the bed, are evaluated by the examiner who uses the Myoton, following the instructions recommended by the manufacturer. The examiner traces an X with a pen on the evaluation point, about 5 cm proximally from the joint line and 1 cm from the anterior edge of the ITB, and then carries out the evaluation which automatically takes place through 3 impulses. The result is automatically stored in the preset instrument with the subject ID.

The parameters measured and stored are:

F – Natural oscillation frequency [Hz], which characterizes the tone or tension S – Dynamic stiffness [N/m]

D – Logarithmic decrease of the natural oscillation, which characterizes the elasticity R – Mechanical stress relaxation time (ms)

C – Ratio of strain and relaxation time, which characterizes the "Creep" (Deborah number).

At the end of all the evaluations, the examiner who manages the Myoton downloads the detected data onto the computer which is automatically stored on an Excel sheet.

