After the manual and instrumental detection, the subjects leave the sampling room and remain in the area for when they will be recalled for the second evaluation.

At a variable distance of 20-60 minutes from the first survey, the tested subjects are recalled, this time only for the manual re-evaluation, in the same way as in the previous evaluation, using a different sequence and identification code from the one used in the first examination.

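### Phase VI puts a pen X on the palpation area between the two manual rounds with no removal step, so second-round ratings may not be made as in round 1 or at baseline

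*Combined protocol and SAP*

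**What the plan says.** Settings gives the order of events. After both examiners have palpated, "the subjects, before getting off the bed, are evaluated by the examiner who uses the Myoton". At that step "The examiner traces an X with a pen on the evaluation point, about 5 cm proximally from the joint line". The subjects then leave the room, and after 20-60 minutes "the tested subjects are recalled, this time only for the manual re-evaluation, in the same way as in the previous evaluation". The only changes named for the second round are a new sequence and a new identification code.

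The Myoton belongs to the last sampling only. Project phases lists "VI phase third manual sampling and evaluation with Myoton", while the III phase entry in Description of the phases reads "First sampling of manual evaluation only, using a sample of 40 subjects (both limbs". The VI phase entry says the manual sampling is repeated "using the same modality of the first evaluation (baseline"), and then: "The same subjects will be tested, after the manual evaluation, with the Myoton".

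The protocol treats the palpation site as something to be standardised. Phase I covers finding the point, and in Phase IV "In vivo evaluation, between operators, are used to verify the exact point of where to take the tension sample".

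The single listed outcome compares agreement at the first and final samplings. Statistical processing plans intra- and inter-examiner weighted kappa on 3 and 7 levels. It does not say which manual round supplies the inter-examiner value.

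**The concern.** A visible X tells both examiners where to put their fingers. Baseline has no such cue, and neither does the first manual round of Phase VI. If the examiners use it, part of any gain in round-2 inter-examiner agreement could come from the mark and not from the training that the study sets out to assess. The Phase VI intra-examiner kappas would compare ratings made under two different conditions. The data could not separate the two explanations afterwards.

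**Working it through.** **Step 1: order of events.** Settings places the Myoton and its X after the first palpation and before the manual-only recall. The VI phase entry says only that the Myoton follows the manual evaluation, directly after describing two evaluations per examiner. Alone, it could mean after both rounds. Settings is specific, so the X falls between the rounds, and the two places should be aligned.

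**Step 2: which samplings carry a mark.** Settings is written as if general, but the III phase entry is manual only and Phase V uses the method of the first sampling. The mark therefore arises only in Phase VI. The Myoton analysis takes a right-left difference, so both limbs are measured and presumably both are marked.

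**Step 3: is the mark hidden?** The X lies about 5 cm above the joint line. Both limbs are bare, the screen starts at the pelvis, and the examiners turn away only while subjects are positioned. No sentence mentions wiping or covering.

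**Step 4: which statistics are reached.**
- Phase VI round-1 inter-examiner kappa: rated before the X, unaffected.
- Phase V decision (kappa of at least 0.60): no Myoton, unaffected.
- Manual-Myoton kappa using round-1 ratings: unaffected.
- Phase VI round-2 inter-examiner kappa, if used alone or averaged in: exposed.
- Every Phase VI intra-examiner kappa: exposed, since it needs both rounds.

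**Step 5: direction, on assumed inputs.** The documents give no figure to reproduce. Assume rating = true side difference (SD 1) + location error (SD 0.7) + perception error (SD 0.7), with no training effect. A mark that is fully followed removes location error in round 2. Since 0.7² = 0.49, the correlations between underlying ratings are:
- inter-examiner, unmarked: 1/(1 + 0.49 + 0.49) = 1/1.98 = 0.51
- inter-examiner, both marked: 1/(1 + 0.49) = 1/1.49 = 0.67
- intra-examiner, unmarked, point varying at random: 1/1.98 = 0.51
- intra-examiner, unmarked, each examiner keeping a habitual point on a subject: 1.49/1.98 = 0.75
- intra-examiner, unmarked against marked, either version: 1/√(1.98 × 1.49) = 0.58

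So round-2 inter-examiner agreement rises. Intra-examiner agreement rises from 0.51 or falls from 0.75, depending on a habit the documents do not describe.

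Simulated with cuts at ±0.43 SD (3 levels, linear weights), the same model gives these kappas:
- inter-examiner: 0.33 to 0.46, or 0.33 to 0.42 if the mark only halves the location error
- intra-examiner: 0.33 to 0.39 (random point) or 0.53 to 0.38 (habitual point). The two end values are the same quantity up to simulation error.
- with the X removed: round 2 equals round 1 (0.33 and 0.33)

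**Step 6: sensitivity.** Two location components (habitual and random) were varied, each with SD between 0 and 0.7, over 3 or 7 levels and linear or quadratic weights. Under full reliance on the mark, the inter-examiner shift ranges from about +0.03 to +0.18 and the intra-examiner shift from about -0.17 to +0.07. A second assumed set (unmarked kappa 0.50; location 10, 25 or 50% of error variance) gives round-2 kappas of 0.52, 0.55 and 0.62, a rise of at most 0.12. The sampling SD of one 3-level kappa at n = 40 is about 0.11 to 0.12. The answer depends on the model, so none of these figures estimates or bounds the effect in this study.

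**The case against.** **Harm is not shown.** It needs three things the documents do not state: the ink is still visible at recall, it lies at or near the palpated point, and the examiners follow it. Coordinates are given only for the Myoton, although Settings calls the site the evaluation point. Wiping off pen may be routine, and the Myoton step follows manufacturer's instructions that are not reproduced. The requirements to repeat round 1 and baseline can be read as implying unmarked limbs. This stands as a limit on the claim. It does not supply a removal step, and followed literally the plan leaves the X in place.

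**Location error may matter little.** The rating compares right with left. Palpating too high or too low on both legs may largely cancel, so only side-to-side inconsistency, or tension that varies differently along each band, adds error. The model in the working ignores this. Phase IV, about 20 hours including work on the exact point, may also have reduced location error. If it had halved location variance in the second assumed set, the mark would add at most 0.01, 0.03 or 0.07. This also stands, and it is why no size is claimed.

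**The outcome may not be touched.** If the inter-examiner kappa uses round 1 only, it is unaffected. That is correct, but the plan does not say so, and the intra-examiner kappas remain exposed.

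A reader might go further and infer that the mark will inflate the training effect, or that intra-examiner agreement will be overstated. The documents support neither: use of the mark is not established, and the intra-examiner bias can go either way.

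**Conclusion.** The procedural gap is real and the consequence is conditional. As written, round 2 of the final sampling may carry a location cue that round 1 and baseline lack, although the plan calls for the same method throughout. If the X is seen and used, round-2 inter-examiner agreement could rise without training, and the Phase VI intra-examiner kappas would mix two conditions with bias of unknown sign. The documents support neither a numerical size nor a statement that the effect is small or large. A reader might also infer that the final-versus-baseline comparison must be limited to round 1. That does not follow: once the X is gone, round 2 is comparable as far as the mark is concerned. This is a minor point, worth acting on because the remedy costs almost nothing and protects the comparability on which the only listed outcome rests.

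**What to change.** In Settings, add that the X is fully removed on both limbs, or covered so that it can be neither seen nor felt, before the subject is recalled for the second manual evaluation. In Description of the phases, VI phase, align the statement on when the Myoton is used with the order in Settings. The cost is a few seconds of wiping per subject by staff already present. Sample size, device, timing and manual-Myoton pairing do not change.

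Only if removal cannot be assured, state in Statistical processing that the final-versus-baseline inter-examiner kappa uses round-1 ratings in both samplings. That gives up the round-2 ratings, half of the inter-examiner data, and does not help the intra-examiner kappas.

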#### Outcomes

The study foresees the following outcome:

verify the increase in the agreement after the specific training (comparison between the agreement of the first sampling and that of the final sampling).

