#### **Material and Methods**

The recruitment phase involves the enrollment of asymptomatic young/adult subjects for pathologies of the lower limbs which, in the opinion of the subject himself or the examiner, make detection difficult.

The number of subjects to be recruited was chosen following the indications provided by the International Academy of Manual/ Musculoskeletal Medicine (Patijn 2019).

The enrollment will take place in three distinct phases, each for every phase of the study which involves the evaluation of subjects. In the first (baseline sampling) 40 subjects will be recruited, in the second (verification

sampling) 20 and in the third (final sampling) 40. Consent will be requested each time. Since it is possible that the same subject is recruited several times (since it is not relevant for the purposes of the assessment whether the subjects are different or the same - Patijn 2019) the total number of subjects involved may vary between a minimum of 40 and a maximum of 100.

MyotonPRO (MyotonPRO-Estonia) is a digital palpation device for the non-invasive measurement of the condition of muscle tone, myofascial stiffness and elasticity with good validity and repeatability of the results both in healthy subjects (Chen et al. 2019) and in pathological subjects (Garcia-Bernal et al. 2021). The device features a mechanical actuator, which delivers a percussive pulse to the myofascial structure and records the response. Subsequently, filtering and digital processing are used to process the data and calculate numerical parameters of muscle tone, biomechanical and viscoelastic properties.

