#### **Statistical processing**

Processing of descriptive data of the subjects (age, weight and height).

Evaluation of intra and inter examiner agreement by means of weighted Cohen's K with use of sampling evaluation divided into 3 intervals (+1, 0, -1) and 7 intervals (+3, +2, +1, 0, -1, -2, -3).

The Myoton data are processed by subtracting the average data of the three measurements (automatically carried out by the instrument) of the right limb from that of the left. The data obtained is categorized into 3 levels to be compared, again using weighted Cohen's K, with the data from the manual evaluation.

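### The one listed outcome, a rise in agreement from first to final sampling, is not tied to a particular weighted kappa and has no interval or decision rule for the change

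*Combined protocol and SAP*

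**What the plan says.** The Outcomes section of the combined protocol and SAP gives one outcome: agreement should increase after training, judged by a "comparison between the agreement of the first sampling and that of the final sampling".

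The Statistical processing section describes "Evaluation of intra and inter examiner agreement by means of weighted" Cohen's K, on a 3-level and a 7-level scale. It adds a kappa for manual against Myoton results, for which "The data obtained is categorized into 3 levels to be compared". It says nothing further about the change between samplings.

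Under Description of the phases, phase IV training includes in vivo work between operators to "compare the tension data obtained for the construction of the agreement". Phase V, on about 20 subjects, allows progress to phase VI if "a good improvement in the agreement is highlighted, compared to the previous sampling (baseline) weighted" Cohen's K of at least 0.60; "otherwise, there will be additional training". Phase VI repeats the first sampling on 40 subjects, "with different or identical subjects of the first sampling".

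Material and Methods sets 40, 20 and 40 subjects and states that "it is not relevant for the purposes of the assessment whether the subjects are different or the same". The Settings section has both examiners rate each subject twice on the same day.

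**The concern.** The listed outcome is a difference between two agreement estimates, but the analysis describes only the separate estimates. A reader of the results would see one kappa beside another, with nothing to say whether the gap exceeds sampling error. With 40 subjects per sampling that error is large, so a training effect could be claimed from chance, or a real one left undecided.

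Two further gaps matter for a difference. Several kappas could serve as the outcome, and their values depend on scale and weights. Subjects may also appear in both samplings, which correlates the two kappas, yet no link between persons across samplings is described.

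**Working it through.** **Inputs from the documents.** n = 40 at first sampling, about 20 at verification, 40 at final sampling; two examiners, two rounds, two scales; gate at 0.60 plus an undefined improvement. No alpha, power, expected kappa or expected rise is stated, so there is no planned figure to reproduce beyond 40 + 20 + 40 = 100, which matches the stated maximum.

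**Assumptions for simulation (not in the documents).** Side difference N(0,1); independent examiner errors; cuts at ±0.5 (3 levels) and ±0.5, ±1.0, ±1.5 (7 levels); error SD set so that the 3-level linear-weighted kappa is 0.4, 0.5 or 0.6; different subjects at each sampling; no training effect.

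**1. Candidate kappas.** Per scale there are two intra-examiner kappas, plus one pooled or two by-round inter-examiner kappas: 3 or 4. Over two scales that is 6 or 8 per sampling.

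**2. Chance rise in one pre-chosen kappa, ignoring the gate.** With equal n and no true change, symmetry gives P(rise) of about 50%. The simulated SD of the change is 0.14-0.16 (one round) or 0.11-0.13 (pooled). For a rise above 0.1, P = 1 − Φ(0.1/SD):
- One round: 1 − Φ(0.1/0.14) = 24%; 1 − Φ(0.1/0.16) = 27%.
- Pooled: 1 − Φ(0.1/0.11) = 18%; 1 − Φ(0.1/0.13) = 22%.

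These agree with the simulated 24-27% and 18-22%.

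**3. After the phase V gate (one round).**

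| True kappa, no training effect | 0.4 | 0.5 | 0.6 |
|---|---|---|---|
| Passes first time (0.60 and any excess over baseline) | 9% | 22% | 39% |
| P(rise given pass), any excess | 50% | 53% | 58% |
| P(rise given pass), margin at least 0.1 | 54% | 61% | 69% |
| P(rise given pass), margin at least 0.2 | 63% | 73% | 80% |
| Of all studies started: passes first time and rises (any excess) | 5% | 12% | 22% |

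The last row is, up to rounding, the first times the second (for example 0.22 × 0.53 = 0.12). If verification is repeated up to three times it becomes 13%, 28% and 41%. Gate and outcome share one baseline, so requiring improvement favours studies whose baseline was low by chance. A gate of 0.60 alone leaves P(rise given pass) at about 50%.

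**4. Weights and scale.** The same simulated examiners score 0.50 (3-level linear), 0.61 (3-level quadratic), 0.48 (7-level linear) or 0.68 (7-level quadratic). Reaching 0.60 can therefore turn on an unstated choice.

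**5. Shared subjects.** Var(K_final − K_first) = Var(K_final) + Var(K_first) − 2 Cov. With different subjects the covariance is zero; with shared subjects it generally is not, so an analysis that ignores the overlap uses the wrong variance.

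**6. Power of an interval rule (lower 95% limit above 0), true change 0.4 to 0.6.** Taking the mid-range SD, Φ(0.2/0.15 − 1.96) = 26% for one round and Φ(0.2/0.12 − 1.96) = 38% pooled, matching the simulated 26% and 38%. With the same 40 subjects in both samplings, pooled power is about 54-56% if they are linked and 38% if they are not.

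**7. False increase under that rule, pooled.** 2.4-3.0% ignoring the gate; after the gate, 3.0-3.2% (any excess), 3.2-6.2% (margin 0.1), 3.3-13% (margin 0.2).

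**The case against.** The plan is not silent. It names the weighted-kappa family, and phase V sets a numerical threshold that stops many studies without a training effect. A reader might infer that about half of all such studies would end in a false claim. The documents do not support that. Outcomes does not say that any rise counts as success, the one-half figure follows from symmetry, and only about 5-22% of such studies pass first time and then show a rise. What stands is that the gate is a rule for progression: it compares about 20 verification subjects with baseline, not first with final sampling, and no limit on retraining is given.

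A reader might also infer severe multiplicity. If all six to eight kappas count equally, at least one rises by chance in 86-92% of studies (gate ignored), but that is the upper end of one reading. If only the pooled inter-examiner kappas on the two scales are candidates, the figure is 59-61%. Since within-examiner agreement is also an aim, the wide reading is possible but not required.

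Nor does it follow that a changed subject mix would explain a rise. All samplings draw on one school's volunteers with the same age and BMI limits, and the documents give no basis for sizing any shift. It remains a limitation to state.

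Finally, pooled power assumes errors independent between rounds. If half or 80% of the error variance persists within an examiner (an assumption), a re-run puts it at about 35% or 32% instead of 39%, still above 26% for one round. This objection stands as a caveat.

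**Conclusion.** The concern holds in this limited form: the sole listed outcome cannot be decided as written, because no kappa and weights are chosen for it and the change has no interval or rule. With no training effect, a pre-chosen kappa rises in about 50% of studies, or about 50-58% of those passing a gate of 0.60 plus any excess over baseline. The one-half figure needs only equal n and no true change; every other percentage rests on the assumed distributions. The statement that reuse of subjects is irrelevant may suit a single kappa but not a difference between two.

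This should be fixed, but it is not a fatal flaw. The introduction's reliability and validation aims do not depend on it.

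**What to change.** 1. **Outcomes.** Name one kappa before data are seen, for example the change (final minus first) in the inter-examiner, 3-level, linear-weighted kappa with both rounds pooled. This suits training aimed at agreement between operators, and the Myoton comparison also uses 3 levels, but another single choice is acceptable. All other kappas, including those by round, are secondary.
2. **Statistical processing.** Report the change with a 95% bootstrap interval that resamples subjects and keeps all of a person's ratings together across rounds and samplings. Conclude an increase only if the lower limit is above 0; otherwise report it as not established. State as a limitation that there is no untrained comparison and that subjects may differ.
3. **Material and Methods; Operators.** Replace the statement on irrelevance. The registration operator keeps a coded list, not shown to the examiners, linking persons across samplings, and the number of common subjects is reported.
4. **Phase V.** Use the same kappa and weights, state the improvement margin in advance, and do not count the phase V result as evidence of the increase. Dropping the improvement condition is optional: it removes the selection on a shared baseline but lets more studies without an effect proceed (pooled first pass 38% to 47% at kappa 0.6).

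**Cost.** A few lines of R and one list, with no extra subjects or measurements. The list is an identifying key and may need a line in the consent information. The interval may well include 0, since power for 0.4 to 0.6 is only about 38% pooled with different subjects, and lower if examiner errors persist between rounds. Bare estimates would hide that imprecision.
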